## 8 Safety and Adverse Events

### 8.1 Definitions

#### 8.1.1 Unanticipated Problems Involving Risk to Subjects or Others

Any incident, experience, or outcome that meets all of the following criteria:

- Unexpected in nature, severity, or frequency (i.e. not described in study-related documents such as the IRB-approved protocol or consent form, the investigators brochure, etc)

- Related or possibly related to participation in the research (i.e. possibly related means there is a reasonable possibility that the incident experience, or outcome may have been caused by the procedures involved in the research)
- Suggests that the research places subjects or others at greater risk of harm (including physical, psychological, economic, or social harm).

### 8.1.2 Adverse Event

An adverse event (AE) is defined as any unfavorable and unintended change in the structure, function, or chemistry of the body, or worsening of a pre-existing condition, temporally associated with the use of a product whether or not considered related to the use of the product. In this study, such changes will be monitored, classified, and summarized, as Clinical or Laboratory AEs. Medical condition/diseases present before starting the investigational drug will be considered adverse events only if they worsen after starting Study Treatment. An unexpected AE is one not identified in the Clinical Investigator's Brochure (CIB) or otherwise not expected from the characteristics of the clinical material.

AEs include the following:

- Pre- or post-treatment complications that occur as a result of protocol mandated procedure during or after the first screening visit (before the administration of study drug)
- Any pre-existing condition that increases in severity, or changes in nature during or as a consequence of the study drug phase of a human clinical trial, will also be considered an AE
- Complications and termination of pregnancy;
- All AEs that occur from the screening visit onwards and throughout the duration of the study, including the follow-up off study treatment period should be recorded as an AE

AEs do not include the following:

- Medical or surgical procedures other than the definitive surgical procedure for Cohort I (e.g., surgery, endoscopy, tooth extraction, transfusion) performed; the condition that leads to the procedure is an AE
- Pre-existing diseases or conditions or laboratory abnormalities present or detected before the screening visits that do not worsen
- Situations where an untoward medical occurrence has not occurred (e.g., hospitalization for elective surgery, social and/or convenience admissions).
- Overdose without clinical sequelae
- Any medical condition or clinically significant laboratory abnormality with an onset date before the consent form is signed and not related to a protocol associated procedure is not an AE. It is considered to be pre-existing and should be documented on the medical history CRF
- Uncomplicated pregnancy (documented on a pregnancy CRF)
- An induced elective abortion to terminate a pregnancy without medical reason (documented on a pregnancy CRF)

### 8.1.3 Serious Adverse Event

A serious adverse event (SAE) is any AE that meets one of the following conditions:

- Death during the period of surveillance defined by the protocol;

- Is immediately life-threatening (e.g., subject was, in the view of the Investigator, at immediate risk of death from the event as it occurred). This does not include an AE that, had it occurred in a more serious form, might have caused death;
- An event requiring inpatient hospitalization or prolongation of existing hospitalization during the period of protocol defined surveillance (including any overnight stay in the hospital, regardless of the length of stay, even if the hospitalization is only a precautionary measure to allow continued observation. However, hospitalization (including hospitalization for an elective procedure) for a pre-existing condition that has not worsened, does not constitute an SAE (see Section 8.1.12);
- Results in congenital anomaly or birth defect;
- Results in persistent or significant disability/incapacity or substantial disruption of the ability to conduct normal life functions;
- Is an important medical event that may not result in death, be life threatening, or require hospitalization, but based upon appropriate medical judgment, may jeopardize the subject and may require medical or surgical intervention to prevent one of the outcomes listed above. Examples of such medical events include allergic bronchospasm requiring intensive treatment in an emergency room or at home for allergic bronchospasm, blood dyscrasias or convulsions that do not result in inpatient hospitalization, or the development of drug dependency or drug abuse; development of malignancies.

#### Clarification of Serious Adverse Events

- Death is an outcome of an AE, and not an adverse event in itself
- The subject may not have been on investigational medicinal product at the occurrence of the event. Dosing may have been given as treatment cycles or interrupted temporarily before the onset of the SAE, but may have contributed to the event
- “Life-threatening” means that the subject was at immediate risk of death from the event as it occurred. This does not include an event that might have led to death if it had occurred with greater severity
- Complications that occur during hospitalizations are AEs. If a complication prolongs the hospitalization, it is an SAE
- Inpatient hospitalization means the subject has been formally admitted to a hospital for medical reasons, for any length of time. This may or may not be overnight. It does not include presentation and care within an emergency department

The investigator should attempt to establish a diagnosis of the event on the basis of signs, symptoms, and/or other clinical information. In such cases, the diagnosis should be documented as the AE and/or SAE and not the individual signs/symptoms.

Serious adverse events that are ongoing should be followed until resolution. The reporting period for SAEs is described in Section 8.3.

#### **8.1.4 Adverse Event Reporting Period**

0-3 days after each Study Treatment. Study subjects will be directly observed by study personnel for 30-45 minutes after administration of Study Treatment for immediate reactions. The occurrence and severity of any AE during this period or the lack of same will be recorded. After

that, subjects will be given an oral thermometer and a Participant Reminder Diary. They will be asked to take and record their body temperature daily at the same time and to note and characterize in their own words any local or systemic events they experience, during this 3 day period after each Study Treatment.

Throughout the Study. In addition to the daily record of oral temperature, administration site reactions, and systemic complaints recorded for 3 days after Study Treatment or until resolution, subjects will be queried at each study visit regarding the occurrence of any SAE or other AE that may have occurred since the last study visit. They will be reminded to contact study personnel and immediately report any such event that occurs during the course of the study. These events will be recorded on the CRFs.

The investigator will grade laboratory AEs and clinical AEs (based on discussions with study participants) with respect to the following levels of severity as defined in the document “Common Terminology Criteria for Adverse Events (CTCAE)”, NCI version 4.03 issued by the US Department of Health and Human Services:

- Mild (Grade 1)
- Moderate (Grade 2)
- Severe (Grade 3)
- Potentially Life Threatening (Grade 4)
- Deaths (Grade 5)

Adverse events should be captured once on the CRF at the maximum severity reported.

### **8.1.5 Causal Relationship of Clinical Material to Adverse Events**

A related AE is one judged to have a suspected relationship to the administration of the clinical material, (INO-3112) and the investigational CELLECTRA® device. An AE may also be assessed as not related to the investigational product. The Investigator is responsible for reporting adverse events and causality (judging the relationship between the administration of the clinical material and a subsequent AE) because the investigator is knowledgeable about the subject (e.g., medical history, concomitant medications), administers the investigational product, and monitors the subject’s response to the investigational product. The Investigator is aware of the subject’s clinical state and thus may be sensitive to distinctions between events due to the underlying disease process versus events that may be product related and may have observed the event. The Sponsor will assess the overall safety of the investigational product and determine whether to report expeditiously to the regulatory agencies.

Investigators should use their knowledge of the Study Subject, the circumstances surrounding the event, and an evaluation of any potential alternative causes to determine whether or not an adverse event is considered to be related to the study drug, indicating "yes" or "no" accordingly. Causality should be assessed by the Investigator as “yes, related” or “no, unrelated” by the following criteria:

- Yes – there is a reasonable possibility that administration of the Study Treatment contributed to the event;
- No – there is no reasonable possibility that administration of the Study Treatment contributed to the event and there are more likely causes.

The following guidance should also be taken into consideration:

- Temporal relationship of event onset to the initiation of study drug;
- Course of the event, considering especially the effects of dose reduction, discontinuation of study drug, or reintroduction of study drug (where applicable);
- Known association of the event with the study drug or with similar treatments;
- Known association of the event with the disease under study;
- Presence of risk factors in the Study Subject or use of concomitant medications known to increase the occurrence of the event;
- Presence of non-treatment-related factors that are known to be associated with the occurrence of the event

For Study Subject receiving combination therapy, causality may be assessed individually for each protocol-mandated therapy or for the combination.

#### **8.1.6 Preexisting Condition**

A preexisting condition is one that is present at the time of signing of Informed consent. A preexisting condition should be recorded as an adverse event if the frequency, intensity, or the character of the condition worsens during the study period.

#### **8.1.7 General Physical Examination Findings**

At screening, any clinically significant abnormality should be recorded as a preexisting condition. At the end of the study, any new clinically significant findings/abnormalities that meet the definition of an adverse event must also be recorded and documented as an adverse event.

#### **8.1.8 Post-study Reporting Requirements**

All AEs and SAEs including deaths, regardless of cause or relationship, must be reported for subjects on study (including any protocol-required post-treatment follow-up).

Investigators are not obligated to actively seek AEs or SAEs beyond the follow up period for subjects. However, if the investigator learns of an AE or SAE that occurs after the completion of termination visit and the event is deemed by the investigator to be related to the study treatment (following the guidelines in Section 8.1.5), he/she should promptly document and report the event to Inovio Pharmaceuticals.

#### **8.1.9 Abnormal Laboratory Values**

Laboratory abnormalities are usually not recorded as AEs or SAEs. However, laboratory abnormalities (e.g., serum chemistry, CBC, coagulation, CPK) independent of the underlying medical condition that require medical or surgical intervention or lead to investigational medicinal product interruption or discontinuation must be recorded as an AE, as well as an SAE, if applicable. In addition, laboratory or other abnormal assessments (e.g., electrocardiogram, vital signs) that are associated with signs and/or symptoms must be recorded as an AE or SAE if they meet the definition of an AE (or SAE) as described in Sections 8.1.2 and 8.1.3. If the laboratory abnormality is part of a syndrome, record the syndrome or diagnosis (e.g., anemia) not the laboratory result (e.g., decreased hemoglobin).

A clinical laboratory abnormality should be documented as an adverse event if any one of the following conditions is met:

- Requires therapeutic intervention or diagnostic tests

- Leads to discontinuation of study treatment
- Has accompanying or inducing symptoms or signs
- Is judged by the investigator as clinically significant

Grade is an essential element of these criteria. Each CTCAE grading term in the current version is a unique representation of a specific event used for medical documentation and scientific analysis and is a single MedDRA Lowest Level Term (LLT).

Investigators are asked to take the CTCAE grading criteria into account when assessing if a laboratory abnormality qualifies as a laboratory AE. Their clinical judgment ultimately determines whether the abnormality in question is “clinically significant (CS)” or “not clinically significant (NCS)” and the severity of the event. CTCAE grading can be used as a reference when making this determination. It is the responsibility of the Investigators to ensure all AEs are accurately reported and graded.

### **8.1.10 Hospitalization, Prolonged Hospitalization or Surgery**

Any adverse event that results in hospitalization or prolonged hospitalization should be documented and reported as a serious adverse event as detailed in 8.1.3. Any condition related to surgery should be documented as an adverse event if the condition meets the criteria for an adverse event.

Neither the condition, hospitalization, prolonged hospitalization, nor surgery are reported as an adverse event in the following circumstances:

- Hospitalization or prolonged hospitalization for diagnostic or elective surgical procedures for a preexisting condition. Surgery should *not* be reported as an outcome of an adverse event if the purpose of the surgery was elective or diagnostic and the outcome was uneventful.
- Hospitalization or prolonged hospitalization required to allow efficacy measurement for the study.
- Hospitalization or prolonged hospitalization for therapy of the target disease of the study, unless it is a worsening or increase in frequency of hospital admissions as judged by the clinical investigator.

## **8.2 Recording of Adverse Events**

At each contact with the subject, the investigator must seek information on adverse events by specific questioning and, as appropriate, by examination. Information on all adverse events should be recorded immediately in the source document, and also in the appropriate adverse event module of the case report form (CRF). All clearly related signs, symptoms, and abnormal diagnostic procedures results should be recorded in the source document, though should be grouped under one diagnosis.

All adverse events occurring during the study period must be recorded. Adverse events will be measured and graded in accordance with the document entitled “Common Terminology Criteria for Adverse Events (CTCAE)”, NCI version 4.03 issued by the US Department of Health and Human Services on June 14, 2010.

All AEs, regardless of severity, seriousness, or presumed relationship to study treatment, must be recorded using medical terminology in source documents and on the CRF. Whenever possible, a diagnosis should be documented, in lieu of symptoms. The source document and the CRF must contain the investigator's opinion concerning the relationship of the AE to study treatment.

AEs should be described with the following attributes:

- Duration (start and end dates)
- Seriousness
- Severity
- Causality
- Action(s) taken
- Outcome

### **8.3 Reporting of Serious Adverse Events and Unanticipated Problems**

Investigators and the protocol sponsor must confirm to the adverse event reporting timelines, formats and requirements of the various entities to which they are responsible, but at a minimum those events that must be reported are those that are:

- related to investigational product(s),
- unexpected, and
- serious or involve risks to subjects or others (see definitions, section 8.1).

If the report is supplied as a narrative, the minimum necessary information to be provided at the time of the initial report includes:

- |                              |  |
|------------------------------|--|
| • Study identifier           | • Current status   |
| • Study Center               | • Whether study treatment was discontinued   |
| • Subject number             | • The reason why the event is classified as serious  |
| • A description of the event | • Investigator assessment of the grade and association between the event and study treatment |
| • Date of onset              |  |

#### **8.3.1 Events Requiring Expedited Reporting**

Events requiring expedited reporting (ERER) will be defined as treatment- or EP-related adverse events including any of the following:

1. Grade 3 or greater injection site pain, tenderness, erythema, and/or induration recorded  $\geq$  1 hour after study treatment (see Table 6.1)
2. Grade 3 or greater fever within 7 days of study treatment
3. Grade 3 or greater systemic symptoms within 7 days of study treatment

as defined in the “Common Terminology Criteria for Adverse Events (CTCAE)”, version 4.03 issued by the US Department of Health and Human Services on June 14, 2010. The worst grade for that particular event is to be documented on the CRFs.

Sites should inform Inovio of any EREER within 72 hours to discuss whether further dosing should continue for that participant.

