### **6.1.2 Visit for Immunotherapy (Pre and Post surgery: Every 3 weeks $\pm$ 3 days)**

Subjects may receive up to 2 doses of immunotherapy prior to surgery and 1-3 doses post-surgery as previously described. All sequential doses will be administered three weeks ( $\pm$ 3 days) apart.

The following study evaluations will be performed **prior to immunotherapy**:

1. Confirmation of p16 positivity or other pathological evidence of oncogenic HPV infection.
2. Medical/Clinical assessment including concomitant medications/treatments.
3. Focused physical examination including, but not limited to vital signs, weight and oxygen saturation.
4. ECOG Performance Status.
5. Review of adverse events.
6. Clinical laboratory testing including, but not limited to: CBC with differential and platelet count, total serum bilirubin, alkaline phosphatase, AST (SGOT), ALT (SGPT), serum creatinine, serum electrolytes, serum calcium and serum albumin.

NOTE: If clinical screening labs (CBC and Chemistry) were performed within 72 hours prior to the subject's first immunotherapy, these labs are not required to be redrawn prior to the subject's first immunotherapy.

7. Urine  $\beta$ -HCG (for women of child bearing potential) up to 72 hours prior to visit.
8. Whole blood and serum for baseline immunologic assays.

The following study evaluations will be performed on the same day **post-immunotherapy**:

1. Injection site reaction assessment within 30-45 minutes after EP.
2. Review of adverse events.
3. Data should be downloaded from the EP device.
4. Distribute participant reminder card to be reviewed at the next visit.

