#### **6.3.4.1 Participant Reminder Card**

Subjects record any post treatment reactions and enter this information on the participant reminder card. The study staff will review the reminder card and assess the reported events for clinical significance.

Study staff should evaluate each unique reminder card entry according to CTCAE guidelines (Version 4.03) and Table 6.1 of the protocol, “Grading Scale for Injection Site Reactions.” Any reminder card entry determined to meet the criteria for a Grade 1 or higher adverse event should be documented as an adverse event unless deemed part of the subject’s ongoing medical history. If the reminder card entry does not meet the criteria of a Grade 1 or higher AE as per the CTCAE guidelines, clinical judgment can be used to determine whether the entry should be recorded as an AE and documented accordingly in the site’s source. For cases where the reminder card entry and final AE reporting (i.e. grading) do not agree, the reasoning should be recorded in the source documents.

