### 8.3.2 Stopping Rules (Criteria for Pausing of Study)

- 8.3.2.1 If at any time during the study one third (1/3) or more subjects experience an EREER assessed as possibly, probably or definitely related to study treatment, further enrollment and study treatments will be on hold immediately until a thorough investigation has been conducted by the Medical Monitors of Inovio and Principal Investigator.
- 8.3.2.2 Any SAE, potentially life threatening AE or death assessed as possibly, probably or definitely related to study treatment, further enrollment and study treatments will be on hold immediately until a thorough investigation has been conducted by the Medical Monitors of Inovio and Principal Investigator and IRB (if applicable).
- 8.3.2.3 If three or more subjects in this study, experience the same grade 3 or 4 adverse event, assessed as possibly, probably or definitely related to study treatment, further enrollment and study treatments will be on hold immediately until a thorough investigation has been conducted by the Medical Monitors of Inovio and Principal Investigator.
- 8.3.2.4 In the event of any unexpected Grade 4 toxicities, assessed as possibly, probably or definitely related to study treatment, further enrollment and study treatments will be on hold immediately until a thorough investigation has been conducted by the Medical Monitors of Inovio and Principal Investigator and IRB (if applicable).
- 8.3.2.5 The study will be on hold for any report of Grade 3 anaphylaxis from immunotherapy/EP in two or more subjects (as graded per “Common Terminology Criteria for Adverse Events (CTCAE)”, version 4.03 issued by the US Department of Health and Human Services on June 14, 2010). Occurrence in three or more subjects will lead to an immediate halt of enrollment and further immunotherapy until full discussion has been conducted by the Medical Monitors of Inovio and Principal Investigator, IRB (if applicable) and the FDA.

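### Expedited fever and systemic events count for 7 days after each dose, but daily temperature and diary entries are prompted for only 3 days

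*Combined protocol and SAP*

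**What the plan says.** Section 8.3.1 lists treatment- or electroporation-related events that need expedited reporting. Two items have a time window: "Grade 3 or greater fever within 7 days of study treatment" and "Grade 3 or greater systemic symptoms within 7 days of study treatment". The site is to tell the sponsor within 72 hours, so that further dosing for that subject can be discussed.

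Section 8.3.2.1 uses these events in a hold rule. Enrolment and dosing pause if one third or more of subjects "experience an EREER assessed as possibly, probably or definitely related to study treatment".

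Section 8.1.4 sets out collection. Subjects receive an oral thermometer and a diary, and are asked for a daily temperature and their own account of local and systemic events "during this 3 day period after each Study Treatment". The same section later describes temperature, site reactions and systemic complaints as "recorded for 3 days after Study Treatment or until resolution". For the rest of the study it relies on questions at each visit and on prompt self-report: "They will be reminded to contact study personnel and immediately report any such event that occurs during the course of the study".

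Section 6.3.4.1 sets no day limit on the card: "Subjects record any post treatment reactions and enter this information on the participant reminder card". Section 8.2 requires specific questioning about adverse events at every contact.

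**The concern.** The window that decides whether an event counts is more than twice as long as the window in which subjects are prompted to record it. No section asks for a temperature on days 4 to 7 from a subject who was well on day 3. A symptom that the subject noticed can be recalled at a later visit. A temperature that nobody took cannot, and fever is graded on temperature.

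Safety is the primary endpoint (section 3.2.1). Expedited events are the only input to rule 8.3.2.1, and the 72-hour notification can begin only once the site knows of the event. What is at stake is completeness and timeliness: a qualifying fever may be recorded late, graded from recall, or not counted.

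**Working it through.** The plan gives no figure for this point. Its one computed design figure (section 7.1, true SAE incidence below 17% if 0 of 20 subjects have one) reproduces as 1 − 0.025^(1/20) = 16.8%, and nothing below affects it.

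**1. Days without a prompt.** Take the dosing day as day 0.
- Counting window (8.3.1): days 1-7. Prompted record (8.1.4): days 1-3.
- Unprompted for a new onset: 7 − 3 = 4 days, 4/7 = 57% of the window.
- A reaction present by day 3 is still followed to resolution, so the gap concerns new onsets only.

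**2. Time to the next scheduled adverse event query.**
- After a dose followed by another three weeks later (6.1.2, 6.2.2): 21 ± 3 = day 18-24. For an onset on days 4-7 the lag is 18 − 7 = 11 to 24 − 4 = 20 days.
- After the last dose (6.1.6, 6.2.3): 14 ± 3 = day 11-17. The lag is 11 − 7 = 4 to 17 − 4 = 13 days.
- After the last pre-surgery dose in Cohort I: Table S1 marks no adverse event review at surgery, so the next listed query is 14 ± 7 days after surgery (6.1.4). If surgery falls s days after that dose, the query comes at day s + 7 to s + 21. The plan does not fix s.

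**3. Thresholds of the hold rules.** I assume that the denominator of 8.3.2.1 is subjects dosed so far. The threshold is the smallest whole number at or above n/3.

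| Subjects dosed | 8.3.2.1: any expedited event | 8.3.2.3: same related Grade 3-4 event |
|---|---|---|
| 3 | 1 | 3 |
| 10 | 4 | 3 |
| 20 | 7 | 3 |
| 25 | 9 | 3 |

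One uncaptured subject changes the outcome of 8.3.2.1 only when the count is exactly one short. From 10 subjects on, a single recurring event such as fever reaches 8.3.2.3 first, and that rule has no 7-day window.

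**4. Could missed events change rule 8.3.2.1?** The documents give neither a rate of expedited events nor a proportion missed, so both are assumed here. The table shows P(X ≥ 7) for X binomial with 20 subjects and probability rate × (1 − proportion missed).

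| Assumed true rate | None missed | 10% missed | 25% missed |
|---|---|---|---|
| 5% | 0.003% | 0.002% | 0.0005% |
| 10% | 0.24% | 0.13% | 0.04% |
| 20% | 8.7% | 5.4% | 2.2% |
| 40% | 75% | 62% | 39% |

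Missed events matter to this rule only at high rates. Section 1.4.1 reports only Grade 1 and 2 events in the two Phase I trials of VGX-3100, which points to the upper rows.

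**5. Who could still benefit.** At v2.1, 19 subjects had more than 6 months of follow-up, and I take these as having finished dosing. That leaves at most 25 − 19 = 6, or 20 − 19 = 1 if enrolment ends at the minimum.

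**The case against.** The strongest reply is that the two windows do different jobs. Three days is prompted collection of early reactions, and seven days defines which related events are expedited. Nothing requires them to be equal, and the plan has a second route for the whole study: self-report at once, questions at every contact, and a card with no stated day limit. The subject is given the thermometer and is not told to return it. A Grade 3 event is hard to overlook. All of this stands, and it limits the effect. It does not supply a temperature on days 4 to 7 from a subject who was not asked for one.

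A reader might infer more than the documents support:

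- **That sections 8.1.4 and 8.3.1 contradict each other, or that recording ends outright on day 3.** They do not conflict, and a reaction under way is recorded until it resolves.
- **That severe events on days 4 to 7 go undetected.** They have no prompt, but they do have other routes to the site.
- **That re-dosing is unprotected.** Adverse event review and a focused examination come before every dose (6.1.2, 6.2.2).
- **That injection-site events share the gap**, because the staff check is an "Injection site reaction assessment within 30-45 minutes after EP" while the expedited criterion starts at 1 hour. That criterion has no 7-day limit. What happens after the check depends on the card, which is not in the documents, and Table 6.1 already asks for the greatest diameter to be recorded.

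It is also fair to say that 8.3.2.3 is the tighter rule for a recurring fever. An unmeasured fever cannot count there either, but the point does limit how much rests on 8.3.2.1.

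**Conclusion.** The point holds as a gap in ascertainment. For new fever and systemic symptoms, 4 of the 7 days that count after each dose have no prompted record, and the next scheduled query may come 4 to 20 days after onset, with the Cohort I pre-surgery dose depending on the surgery date.

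The effect is probably small. Table 1.2 places the common systemic effects soon after injection, fever is not listed there, and the other hold rules do not use the 7-day window. The number of events missed cannot be derived from the documents. The conclusion assumes that the diary in 8.1.4 and the card in 6.3.4.1 are the same instrument, and that the card itself prompts nothing beyond day 3. Sample size and the planned SAE estimate are unaffected. This is a low-cost improvement to consider, not a defect that undermines the trial.

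**What to change.** In section 8.1.4, extend the daily temperature and diary record from 3 to 7 days after each dose, keeping the continuation to resolution, and revise the card to match.

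The cost is 4 more diary days per dose, 4 × 4 = 16 over four doses for each subject, and a new card. No visits or staff are added. If the change is made part-way, collection will differ between earlier and later subjects for little gain in this trial, so the report should state which subjects used the 3-day record and which the 7-day record. The larger benefit would be to a later protocol that reuses these sections.
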